5.4.5 CML progression to accelerated phase (AP) or blast crisis (BC)

For the evaluation of CML progression to AP or BC, the following criteria will be used. Accelerated phase (AP) is defined by any of the following:

- $\geq 15\%$ blasts in the peripheral blood or bone marrow aspirate, but $< 30\%$ blasts in both the peripheral blood and bone marrow aspirate
- $\geq 30\%$ blasts plus promyelocytes in peripheral blood or bone marrow aspirate, but $< 30\%$ blasts in both the peripheral blood and bone marrow aspirate
- $\geq 20\%$ basophils in the peripheral blood
- Thrombocytopenia ($< 100 \times 10^9/L$) that is unrelated to therapy*

Blast crisis (BC) is defined by any of the following:

- $\geq 30\%$ blasts in peripheral blood or bone marrow aspirate
- Appearance of extramedullary involvement other than hepatosplenomegaly proven by biopsy (i.e., chloroma).

The second bullet for BC cannot be considered in this study as this information was not collected.

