5.1 Inclusion criteria

Participants eligible for inclusion in this study must meet **all** the following criteria:

1. Signed informed consent must be obtained prior to participation in the study
2. Male or female patients with a diagnosis of CML-CP \geq 18 years of age
3. Patients must meet all the following laboratory values at the screening visit:
 - $< 15\%$ blasts in peripheral blood and bone marrow
 - $< 30\%$ blasts plus promyelocytes in peripheral blood and bone marrow
 - $< 20\%$ basophils in the peripheral blood
 - $\geq 50 \times 10^9/L$ ($\geq 50,000/mm^3$) platelets
 - Transient prior therapy related thrombocytopenia ($< 50,000/mm^3$ for ≤ 30 days prior to screening) is acceptable
 - No evidence of extramedullary leukemic involvement, with the exception of hepatosplenomegaly
4. Prior treatment with a minimum of 2 prior TKIs (i.e. imatinib, nilotinib, dasatinib, bosutinib, radotinib or ponatinib)
5. Warning or failure (adapted from the 2020 ELN Recommendations) or intolerance to the most recent TKI therapy at the time of screening
 - Warning is defined as:
 - Three months after the initiation of treatment: BCR-ABL1 $> 10\%$ IS
 - Six months after the initiation of treatment: BCR-ABL1 $> 1-10\%$ IS
 - Twelve months after the initiation of treatment BCR-ABL1 $> 0,1-1\%$ IS

- At any time after the initiation of therapy BCR-ABL1 >0.1-1% IS, loss of MMR (>0.1% with 5-fold increase of BCR-ABL1 transcripts).
 - In addition, patients with failure of treatment according to the ELN 2020 recommendations will be eligible:
 - Three months after the initiation of treatment: BCR-ABL1 > 10% IS if confirmed within 1-3 months
 - Six months after the initiation of treatment: BCR-ABL1 >10% IS
 - Twelve months after the initiation of treatment BCR-ABL1 >1% IS
 - At any time after the initiation of therapy BCR-ABL1 >1% IS, emergence of resistance mutations, high-risk ACA
 - Intolerance is defined as:
 - Non-hematologic intolerance: Patients with grade 3 or 4 toxicity while on therapy, or with persistent grade 2 toxicity, unresponsive to optimal management, including dose adjustments (unless dose reduction is not considered in the best interest of the patient if response is already suboptimal)
 - Hematologic intolerance: Patients with grade 3 or 4 toxicity (absolute neutrophil count [ANC] or platelets) while on therapy that is recurrent after dose reduction to the lowest doses recommended by manufacturer

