- In the event of disease progression, the patient must be discontinued from the study treatment. The following events are considered disease progression.
 - CML-related death (any death during treatment or follow-up if the principal cause of death is marked as “study indication” in the eCRF by the investigator, or if the death occurred subsequent to documented progression to AP/BC and the cause of death is reported as “unknown” or not reported by the investigator)
 - Accelerated phase (AP) as defined by any of the following:
 - $\geq 15\%$ blasts in the peripheral blood or bone marrow aspirate, but $< 30\%$ blasts in both the peripheral blood and bone marrow aspirate
 - $\geq 30\%$ blasts plus promyelocytes in peripheral blood or bone marrow aspirate
 - $\geq 20\%$ basophils in the peripheral blood
 - Thrombocytopenia ($< 100 \times 10^9/L$) that is unrelated to therapy
 - Blast crisis (BC) as defined by any of the following:
 - $\geq 30\%$ blasts in peripheral blood or bone marrow aspirate
 - Appearance of extramedullary involvement other than hepatosplenomegaly proven by biopsy (i.e., chloroma).

Any value of AP or BC within the first 4 weeks of study treatment is not defined as progression to AP/BC within the study unless the subject discontinues study treatment due to progression.

If discontinuation from study treatment occurs, the investigator should make a reasonable effort to understand the primary reason for the participant’s premature discontinuation of study treatment and record this information.

Participants who discontinue from study treatment agree to return for the end of treatment and follow-up visits indicated in the Assessment Schedule (refer to [Section 8](#)).

If the participant cannot or is unwilling to attend any visit(s), the site staff should maintain regular telephone contact with the participant, or with a person pre-designated by the participant. This telephone contact should preferably be done according to the study visit schedule.

After discontinuation from study treatment, at a minimum, in abbreviated visits, the following data should be collected at clinic visits or via telephone/email contact:

- New / concomitant treatments
- Adverse Events / Serious Adverse Events

The investigator must also contact the IRT to register the participant's discontinuation from study treatment.

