12.8 Sample size calculation

12.8.1 Primary endpoint(s)

A sample size of 156 patients (randomized to either asciminib 40 mg b.i.d. or 80 mg q.d.) will have 80% power to reject the null proportion of 23% (upper limit of 95% exact binomial CI of the MMR rate at Week 48 in Bosutinib arm in ASCEMBL: see below) at 0.025 one-sided level of significance if the true rate (under alternative hypothesis) is 33% (considering a clinically meaningful difference of 10% or more) using exact test for single proportion (nQuery 7).

[The MMR rate (95% CI) at Week 48 in Bosutinib arm of ASCEMBL trial (at primary analysis) was 11.1 % (4.2% – 22.6%; 54 patients were eligible for this sample size computation)].

An additional 30 patients (randomized to either asciminib 40 mg b.i.d. or 80 mg q.d.) intolerant only to last TKI and in MMR at baseline will also be analyzed.

13 Ethical considerations and administrative procedures

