2.6.1 Secondary endpoint(s)

No statistical testing of secondary efficacy endpoints will be performed.

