5.4.7 Disease progression

The following events are considered disease progression

- CML-related death (any death during treatment or follow-up if the principal cause of death is marked as “study indication” in the eCRF by the investigator, or if the death occurred subsequent to documented progression to AP/BC and the cause of

death is reported as “unknown” or not reported by the investigator)

- Accelerated phase (AP) as defined by any of the following:
 - o $\geq 15\%$ blasts in the peripheral blood or bone marrow aspirate, but $< 30\%$ blasts in both the peripheral blood and bone marrow aspirate
 - o $\geq 30\%$ blasts plus promyelocytes in peripheral blood or bone marrow aspirate
 - o $\geq 20\%$ basophils in the peripheral blood
 - o Thrombocytopenia ($<100 \times 10^9/L$) that is unrelated to therapy
- Blast crisis (BC) as defined by any of the following:
 - o $\geq 30\%$ blasts in peripheral blood or bone marrow aspirate
 - o Appearance of extramedullary involvement other than hepatosplenomegaly proven by biopsy (i.e., chloroma).

Any value of AP or BC within the first 4 weeks of study treatment is not defined as progression to AP/BC within the study unless the subject discontinues study treatment due to progression.

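### The AP/BC event is defined inconsistently: isolated extramedullary blast crisis is listed as progression but was not collected, and a platelet count accepted at entry can later be scored as accelerated phase

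*SAP*

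**What the plan says.** **Extramedullary blast crisis.** SAP 5.4.5 gives two criteria for blast crisis, then says of the extramedullary one: "The second bullet for BC cannot be considered in this study as this information was not collected". SAP 5.4.7, which defines disease progression, lists the same criterion without a caveat: "Appearance of extramedullary involvement other than hepatosplenomegaly proven by biopsy (i.e., chloroma"). Protocol 9.1.1 lists it too and requires treatment to stop on progression. In protocol Table 8-1, extramedullary involvement is a database item at screening only, and physical examinations are kept as source data only. The censoring rules for PFS and TTF (SAP 2.6.1.3 and 2.6.2) nevertheless name an extramedullary assessment as a possible last-assessment date.

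**Platelets.** Protocol 5 says the inclusion criteria outline the chronic-phase definition. Criterion 3 in protocol 5.1 accepts platelets of 50 x 10^9/L or more, and below that only "Transient prior therapy related thrombocytopenia" of at most 30 days. AP includes platelets below 100 x 10^9/L "that is unrelated to therapy" (protocol 9.1.1; also SAP 5.4.5 and 5.4.7). AP or BC values in the first 4 weeks do not count unless treatment is stopped for progression.

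**Where the event is used.** PFS and TTF (SAP 2.6.1.3), duration of MMR (SAP 2.6.1.1 and 2.6.2) and treatment failure (SAP 5.4.4). Under SAP 2.5, treatment failure before Week 48 cancels an MMR at Week 48. The secondary endpoints are descriptive: "No statistical testing of secondary efficacy endpoints will be performed".

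**The concern.** Two analysts working from SAP 5.4.5 and SAP 5.4.7 would classify the same patient differently. Because the data were not collected, 5.4.5 wins by default. A patient taken off treatment for isolated extramedullary blast crisis then contributes a censoring time, not an event. That censoring is informative: follow-up ends because the disease progressed.

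The platelet criterion can err the other way. A patient may be accepted as chronic phase with a count of 50-99, keep that count, and be scored as AP at a visit after Week 4. Such a patient adds a progression event without any change in disease. If this happens before Week 48, it can also turn an MMR into a non-response.

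**Working it through.** **1. The plan's own figure.** Protocol 12.8.1: "A sample size of 156 patients" "will have 80% power to reject the null proportion of 23"% "at 0.025 one-sided level of significance if the true rate (under alternative hypothesis) is 33"%. With the exact binomial test and n = 156, the smallest responder count r with P(X >= r | 0.23) <= 0.025 is 47 (47/156 = 30.1%). Exact alpha is 0.0241 and power, P(X >= 47 | 0.33), is 80.1%. The figure reproduces and is not in dispute. The Clopper-Pearson lower limit is 23.05% at 47 responders and 22.47% at 46, so a few responder calls matter only if the count falls near 47.

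**2. Entry limits against AP limits.**

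| Measure | Entry (protocol 5.1) | AP (protocol 9.1.1; SAP 5.4.5, 5.4.7) | Overlap |
|---|---|---|---|
| Blasts | <15% | >=15% | none |
| Blasts plus promyelocytes | <30% | >=30% | none |
| Basophils | <20% | >=20% | none |
| Platelets (x 10^9/L) | >=50 | <100 and unrelated to therapy | 50-99 |

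Only platelets overlap. The entry criterion asks about therapy-relatedness only below 50. Two conditions narrow the gap:
- The 4-week rule delays scoring but then expires, while hematology continues at later visits.
- The attribution condition has no stated data source or assessor, and the text does not say whether therapy includes earlier TKIs. In SAP 5.4.5 the bullet carries an asterisk with no visible footnote.

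**3. What happens to isolated extramedullary blast crisis under SAP 5.4.5.**
- PFS: no event; censored at the last assessment.
- Duration of MMR: no event; censored at the last on-treatment PCR.
- TTF: no event through the AP/BC line. The introduction to TTF says discontinuation was added as an event, but the list beneath it does not include it. The patient is censored if the list governs and no other failure line is met.
- Week 48 MMR: no distortion. A stop before Week 48 is a non-response for any reason (SAP 2.5.3).

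**4. What happens to a baseline count of 50-99 scored as AP after Week 4.** It is an event in PFS, in TTF as the SAP lists it, and in duration of MMR if the patient has reached MMR. Before Week 48 it is also treatment failure, so a Week 48 MMR does not count. The protocol's own TTF bullets (12.5.1) do not list AP/BC.

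**5. Size.** One patient is 1/156 = 0.64 percentage points. The documents do not give the share f enrolled at 50-99, or the share g of those judged unrelated to therapy and still low after Week 4. As an illustration on assumed values, spurious events = 156 x f x g. If every one fell before Week 48 in patients who would respond at the same 33%, the counted rate would be 0.33 x (1 - f x g).

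| f | g | Spurious AP events | Counted MMR rate | Power at r = 47 |
|---|---|---|---|---|
| any | 0 | 0 | 33.0% | 80.1% |
| 2% | 50% | 1.6 | 32.7% | 77.6% |
| 5% | 25% | 2.0 | 32.6% | 76.9% |
| 10% | 50% | 7.8 | 31.4% | 65.8% |

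These rows show sensitivity, not an estimate. The first row is possible. The number of isolated extramedullary blast crises is also unknown.

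**The case against.** The strongest reply is that three tempting readings go too far.

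- **A reader might infer that patients enrolled at 50-99 already meet AP.** They do not. AP also requires the low count to be unrelated to therapy. Every patient has had at least two TKIs and then takes asciminib. In ASCEMBL, thrombocytopenia of Grade 3 or more was the most common adverse event on asciminib (17.3%, protocol 1.1). Many low counts will have a treatment explanation. Protocol 5.2 also excludes a known history of AP/BC, and PFS requires documented progression. Over-counting is a risk that depends on attribution, not an established error.
- **A reader might infer that extramedullary blast crisis can never be counted.** A case with 30% blasts or more counts under the other blast-crisis criterion. Any death is a PFS event, and a CML-related death ends duration of MMR. Only the isolated case is lost, and SAP 5.4.5 discloses this openly.
- **A reader might infer a definite excess of a few percentage points of false progression.** No figure in the documents supports one, and any range must include zero.

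It can also be said that the missing footnote in SAP 5.4.5 may hold the attribution rule. If so, that part of the point falls. Finally, the endpoints mainly affected are untested.

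All of this limits the size of the point. It does not remove the conflict between SAP 5.4.5 and 5.4.7, or supply a baseline rule for platelets.

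**Conclusion.** The point holds in limited form. The contradiction over extramedullary blast crisis is plain on the page, and its consequence, informative censoring of isolated cases, follows directly for PFS and duration of MMR. For TTF it depends on whether discontinuation counts as an event. The platelet overlap is also real. It becomes a false AP event only if a count present at baseline is judged unrelated to therapy and persists past Week 4.

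The size cannot be computed. It is 0.64 percentage points per patient on 156, and the number of patients may be zero. The effect falls on descriptive secondary endpoints. Only the platelet half can reach the primary endpoint, through the treatment-failure rule, and then for perhaps a few responder calls. The stated sample size and power stand.

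**What to change.** These changes concern how events are counted in the analysis. No clinical threshold or stopping rule is proposed; the sponsor must reconcile protocol 5.1 and 9.1.1 with each other and with the SAP.

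1. Reconcile SAP 5.4.5 and 5.4.7 so that one AP/BC definition feeds PFS, TTF, duration of MMR and SAP 5.4.4.
2. Review, before database lock, every subject whose Disposition reason is disease progression. Count those confirmed as AP/BC, including extramedullary blast crisis. Add a sensitivity analysis that counts all such stops. Review is needed because protocol 10.1.1 places loss of response under progression of malignancy, so the Disposition reason alone would overcount.
3. Do not count thrombocytopenia already present at baseline as an AP event on its own; the other AP criteria still apply to these subjects. State the data source for attribution to therapy, and restore or delete the asterisk in SAP 5.4.5.
4. Correct the extramedullary term in the PFS and TTF censoring rules, since no post-screening assessment is scheduled for the database. Keep extramedullary disease in the CHR definition, where spleen and liver are part of the criterion.

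The cost is SAP wording and a short case review. The SAP already summarizes the Disposition reason (2.3.1), and baseline platelets are collected. The downside is some reliance on investigator-reported progression. In addition, a true AP shown only by a further platelet fall, in a subject already low at baseline, would be counted only if it led to a progression stop that the review confirms.

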5.4.6 CML-related deaths

CML-related death is considered as any death during treatment or follow-up

- if the principal cause of death is marked as “study indication” in the eCRF by the investigator,
- or if the death occurred subsequent to documented progression to AP/BC and the cause of death is reported as “unknown” or not reported by the investigator.

With respect to the second bullet, as “unknown” cause of death will be coded to the Medical Dictionary for Regulatory Activities (MedDRA) preferred term ‘Death’, this MedDRA coding will be used in the derivation of CML-related death.

5.4.7 Disease progression

The following events are considered disease progression

- CML-related death (any death during treatment or follow-up if the principal cause of death is marked as “study indication” in the eCRF by the investigator, or if the death occurred subsequent to documented progression to AP/BC and the cause of

death is reported as “unknown” or not reported by the investigator)

- Accelerated phase (AP) as defined by any of the following:
 - o $\geq 15\%$ blasts in the peripheral blood or bone marrow aspirate, but $< 30\%$ blasts in both the peripheral blood and bone marrow aspirate
 - o $\geq 30\%$ blasts plus promyelocytes in peripheral blood or bone marrow aspirate
 - o $\geq 20\%$ basophils in the peripheral blood
 - o Thrombocytopenia ($<100 \times 10^9/L$) that is unrelated to therapy
- Blast crisis (BC) as defined by any of the following:
 - o $\geq 30\%$ blasts in peripheral blood or bone marrow aspirate
 - o Appearance of extramedullary involvement other than hepatosplenomegaly proven by biopsy (i.e., chloroma).

Any value of AP or BC within the first 4 weeks of study treatment is not defined as progression to AP/BC within the study unless the subject discontinues study treatment due to progression.

5.4.8 Overall survival

This includes all deaths.

5.5 Derivation of response rates and categories

5.5.1 Response rate at a specific time point

The molecular and cytogenetic response evaluations will be summarized by the following mutually exclusive categories which are based on the respective assessment within the time window:

- **Response categories** (sections 5.4.1 and 5.4.2): Subjects with an available assessment at that time point (+/- time window) indicating any of the response categories.
- **No response:** Subjects with assessment at that time point (+/- time window) indicating 'no response'
- **Missing:** Subjects without an evaluable response assessment at that time point (+/- time window). This category is then further split into subjects who are ongoing without treatment failure at the beginning of the relevant time window, subjects who are ongoing with treatment failure at the beginning of the relevant time window, subjects who discontinued due to lack of efficacy, disease progression (PD) or death and subjects who discontinued due to other reasons.

5.6 Statistical models

5.6.1 Analysis supporting primary objective(s)

The null hypothesis that proportion of subjects who achieve MMR equals to 0.23 at 48 weeks will be tested against one-sided alternative.

The statistical hypotheses are:

$$H_0: \pi=0.23 \text{ vs. } H_1: \pi >0.23$$

where π is the proportion of subjects who achieve major molecular response (BCR::ABL1 \leq 0.1% IS) rate at Week 48. MMR rate and its 95% confidence interval based on the Clopper-Pearson method will also be presented.

The proportion test will be implemented via SAS procedure FREQ with binomial option in the TABLES statement. The p-value corresponding to the proportion test will be used which follows a standard normal distribution.

The setup of the data is important. PROC FREQ will run a binomial test assuming that the probability of interest is the first level of the variable (in sorting order) in the TABLES statement. For example, the above statements run a binomial test on MMR flag, which takes one of two numeric values – 1 (Yes) or 0 (No). The binomial test is applied to MMR flag values of 1 because it is the first sorted value for that variable.

Confidence interval for MMR rate

MMR will be summarized in terms of percentage rates with 95% confidence interval using exact binomial confidence interval (implemented using SAS procedure FREQ with EXACT statement for one-way table ([\[Clopper and Pearson 1934\]](#))).

5.6.2 Analysis supporting secondary objective(s)

Kaplan-Meier estimates

An estimate of the survival function will be constructed using Kaplan-Meier (product-limit) method as implemented in PROC LIFETEST with METHOD=KM option. The PROC LIFETEST statement will use the option CONFTYPE=LOGLOG.

Median survival will be obtained along with 95% confidence intervals calculated from PROC LIFETEST output using the method of [\[Brookmeyer and Crowley 1982\]](#). Kaplan-Meier estimates of the survival function with 95% confidence intervals at specific time points will be summarized. The standard error of the Kaplan-Meier estimate will be calculated using Greenwood's formula [\[Collett 1994\]](#).

Cumulative incidence

The cumulative incidence proportion (CIP) will be estimated using competing risk analysis via SAS procedure LIFETEST or PHREG with EVENTCODE=Code for event of interest (e.g. MMR) as option in the MODEL statement, whereas code=0 for censored subjects and any other code (e.g. code=2) for subjects who dropped out due to a competing risk. The estimated CIP at the defined time points will be presented with 95% CI together with number of subjects with events, number of subjects with competing risks, and number of subjects censored.

6 Reference

Branford S, Hughes T (2006) Diagnosis and monitoring of chronic myeloid leukemia by qualitative and quantitative RT-PCR. *Methods Mol Med*; 125:69-92.

Brookmeyer R and Crowley J (1982). A Confidence Interval for the Median Survival Time. *Biometrics*, 38, 29 - 41.

Clopper, C. J., & Pearson, E. S. (1934). The use of confidence or fiducial limits illustrated in the case of the binomial. *Biometrika*, 26(4), 404-413.

Collet D (1994). *Modelling survival data in medical research*. London, Chapman & Hall.

FDA (2020). *Statistical Considerations for Clinical Trials During the COVID-19 Public Health Emergency. Guidance for Industry*.

Hughes, T., & Branford, S. (2006). Molecular monitoring of BCR–ABL as a guide to clinical management in chronic myeloid leukaemia. *Blood reviews*, 20(1), 29-41.

